11.4. Treatment Adherence

Adherence to therapy with ASV is determined by evaluating the usage data from the AirCurve device in AirView. Additionally, discussion with the subject will indicate issues with the mask or other barriers to use. See Appendix I.

11.5. Subject Discontinuation Criteria

If, after 30 days after initiation of therapy, a subject has not met the adherence criteria of at least 4hrs ASV usage per day (24hr period) for 70% of the days enrolled (excluding days spent in the hospital), they will be discontinued from the study. Follow procedures for Device and Subject Disposition in Section 11.6. Record the number of hospitalizations and date of discontinuation on the end of study eCRF.

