9. THERAPY

9.1. Treatment with Adaptive Servo-ventilation (AirCurve)

The AirCurve device will be used at home; however the therapy can be initiated in the hospital or as an outpatient within 14 days of hospital discharge. Although the AirCurve has three therapy modes, CPAP, ASV, and ASVAuto, only the ASVAuto mode will be used for this study. Subjects are advised to use the AirCurve device during any significant sleeping period, including naps. Ideally, AHI should be at or below 5 e/hr. However, if the AHI cannot be maintained below 10 e/hr, the subject's therapy should be adjusted (mask and/or pressure settings).

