10. STUDY SCHEDULE

10.1. Study Entry

A patient meets eligibility criteria of the study if all of the inclusion criteria and none of the exclusion criteria are met. Subjects will stay enrolled for the duration of the study even if they are re-hospitalized during their enrollment.

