10.5. Detailed Visit Schedule

The following visit schedule applies to subjects who met all eligibility criteria, and are enrolled in the CAT-PEF Feasibility Study.

10.5.1. Visit 1: Screening/Baseline	Primary Responsibility	
	Cardiology	Sleep
Determination of eligibility	X	
ApneaLink Test		X
Mask fitting, ASV set-up and training, myAir set-up		X
Document demographics and baseline data	X	
KCCQ-12	X	

10.5.2. ASV Adherence Monitoring	Primary Responsibility	
	Cardiology	Sleep
Follow-up with subject 2-3 days after start of therapy		X
Review AirView for adherence flags weekly		X
Contact subjects with sub-optimal adherence as needed		X
Review overall adherence at 30 days post-therapy start. Subjects not meeting adherence criteria will be discontinued from the study		X
Document contact in EDC		X

10.5.3. Visit 2: End of study Follow-up	Primary Responsibility	
	Cardiology	Sleep
Collect follow up data on death and hospitalizations	X	
Disposition AirCurve device and refer to sleep therapist		X
KCCQ-12	X	

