10.6. Overview of visits

	Screening	Baseline "Day 0" (≤3 days from AL report)	2-3 days Post-device start	30 days (±2 days) "1 mo"	Weekly during study	12 weeks (±2 weeks) "3 mo"
Visit Location:	Hospital or Clinic	Hospital or Clinic	Phone call			Clinic or Phone Call
Review of HF history, signs & symptoms	X					
ApneaLink Air test	X					
ASV therapy and mask tolerance	X					
KCCQ-12	X					X
Initiation of ASV Therapy		X				
ASV Device use monitoring			X	X*	X	X

*Check to confirm adequate device use

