12.1. Hospitalization

For this protocol, the definition of hospitalization is in-patient care of more than one calendar day (overnight admission). The number of hospitalizations the occurred during a subject's participation in the study will be recorded at the final visit.

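### Does the protocol leave the 30-day evaluability check without the hospital days it must exclude?

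*Combined protocol and SAP*

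**What the plan says.** The 30-day criterion is written out four times. Sections 11.5 and 13.1 count 24-hour days: "at least 4hrs ASV usage per day (24hr period) for 70% of the days enrolled (excluding days spent in the hospital". Sections 4 and 7.2.2 count nights and leave out hospital nights. The criterion decides both who is discontinued and who belongs to the 160 evaluable subjects.

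On hospital data, section 11.5 asks sites to "Record the number of hospitalizations and date of discontinuation on the end of study eCRF". Section 12.1 has the number of hospitalizations during a subject's "participation in the study will be recorded at the final visit". Section 10.5.3 lists, under Cardiology at Visit 2, "Collect follow up data on death and hospitalizations".

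At 30 days, section 10.5.2 gives the Sleep team this task: "Review overall adherence at 30 days post-therapy start. Subjects not meeting adherence criteria will be discontinued from the study". The footnote to the 30-day column in section 10.6 reads only "Check to confirm adequate device use".

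Hospital days inside the window are foreseeable. Under section 9.1 "the therapy can be initiated in the hospital or as an outpatient within 14 days of hospital discharge", and under section 10.1 "Subjects will stay enrolled for the duration of the study even if they are re-hospitalized during their enrollment".

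**The concern.** The denominator of the criterion is 30 minus the hospital days, so someone must know those days when the decision is made. The visit schedule does not list them at day 30. The named record is a count, and it is taken at or after the decision. One stay of 2 days and one stay of 10 days give the same count but different denominators. AirView reports usage, leak and AHI (section 9.3) and cannot by itself tell a hospital night from a night of non-use at home.

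If the days were missed, the error would run one way: good users with an early stay would be dropped as non-adherent. The evaluable set would then be selected against early hospitalization, and an average number of hospitalizations estimated in that set (section 13.3) would be too low.

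**Working it through.** **1. The plan's own figures.** Inputs from section 13.1: SD 1.6 h, 95% confidence, 160 evaluable, 60% evaluable.
- Margin of error: 1.96 × 1.6 / √160 = 0.248 h (0.2498 h with the t quantile). The stated 0.25 h or less is reproduced.
- Enrolment: 160 / 0.60 = 266.7, against 266 stated, rounded up to 300.
- Room above target: 300 × 0.60 − 160 = 20.

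**2. What the exclusion is worth.** With *h* hospital days and no qualifying use on them, the criterion needs ceil(0.7 × (30 − h)) home days. If the 30 days stay in the denominator, it needs 21.

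| h | Home days | Needed, days excluded | Needed, not excluded | 21 as share of home days |
|---|---|---|---|---|
| 0 | 30 | 21 | 21 | 70.0% |
| 1 | 29 | 21 | 21 | 72.4% |
| 2 | 28 | 20 | 21 | 75.0% |
| 3 | 27 | 19 | 21 | 77.8% |
| 5 | 25 | 18 | 21 | 84.0% |
| 7 | 23 | 17 | 21 | 91.3% |
| 10 | 20 | 14 | 21 | cannot pass |

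The exclusion matters for stays of 3 days or more. At 1 day it changes nothing, and at 2 days it moves the bar by one day.

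**3. Would the site know the days?**
- Section 11.5 itself orders them excluded. Whoever applies the rule has to ask.
- Appendix I: AirView is reviewed at least weekly, and 3 or more nights under 3 h prompt contact with the subject. A stay of 3 or more nights without use meets that trigger; the stays it misses are those for which step 2 shows little or no effect. A stay at the very end of the window may fall between weekly reviews, but it shows as a gap in the usage reviewed at day 30.
- Contacts go on the Adherence Follow Up Call CRF (Appendix I) and into EDC (section 10.5.2). Section 11.4 expects talks with the subject to reveal barriers to use.
- Section 14.1 requires progress notes covering all data the protocol requires. Section 12 has event information entered in the eCRF, and section 17.1 requires timely SAE reporting.
- Index stay: sections 9.1 and 10.4 set limits counted from discharge and from the first encounter, so sites already need those dates.
- Section 10.5 assigns primary responsibility, not sole access. Section 16.1 requires both specialties at each site, and Appendix I says the sleep therapist cannot exclude subjects.

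**4. Size if every site ignored the exclusion.** The documents give no stay rate or length. Assumptions: 10% to 30% of 300 subjects have one stay of 3 to 7 days; no use in hospital; subject means normal with SD 1.6 h; night-to-night SD 1 or 2 h; mean set so that 60% pass without hospital days. Subjects changed = 300 × stay rate × (pass rate with exclusion − pass rate without).
- Smallest (3 days, SD 1 h): 300 × 0.10 × (0.598 − 0.545) = 1.6.
- Largest (7 days, SD 2 h): 300 × 0.30 × (0.553 − 0.271) = 25.4.
- At 5 days: 2.8 to about 16.

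In the largest case the evaluable number falls from 300 × (0.7 × 0.60 + 0.3 × 0.553) = 175.8 to 300 × (0.7 × 0.60 + 0.3 × 0.271) = 150.4. The margin becomes 1.96 × 1.6 / √150.4 = 0.256 h. In the same model, mean use among retained subjects rises by about 0.11 h, inside the planned margin.

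**5. Partial failure.** The loss scales with the share of stays overlooked. In the largest case the set drops below 160 only if more than (175.8 − 160) / 25.4 = 62% of stays are overlooked.

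**The case for a change.** The best case for a change is that nothing ties these records to the 30-day check. Section 12 names no admission or discharge dates and sets no day-30 deadline. Contact under Appendix I is at the therapist's discretion. Up to 10 centers may look up the days in different ways. If therapy starts during the index stay, the secondary endpoint, which counts stays after study entry, may not register that stay at all. In the worst modelled case the share of retained subjects with an early stay falls by 48.5% in relative terms (11.8% to 28.8% at 5 days). Two date fields per stay would close the matter without a new visit.

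What stands is that the protocol does not explicitly schedule these dates, and naming them would be tidier. The rest is weaker. The eCRF and the Manual of Procedures are not part of the documents, so the count in sections 11.5 and 12.1 cannot be taken as all that is recorded. It matches the secondary endpoint, and the Visit 2 item is worded more broadly. A later re-derivation is not closed off either, since device data are transmitted after each use and source records are kept. The bias in the hospitalization average is conditional: section 13.3 does not restrict it to evaluable subjects, and section 11.5 records the count for discontinued subjects as well.

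The four statements also differ in unit (night or 24-hour day) and in the start of the window (study entry in section 4, therapy or ASV use elsewhere). That is a separate matter of wording, which the sponsor must reconcile; it does not affect whether hospital days can be known. Section 10.6 puts the start of therapy at baseline, day 0, so the two starting points may lie close together.

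**Conclusion.** No change to the plan follows. The protocol leaves out a data-capture detail that a site following section 11.5 would supply: the rule names the exclusion, weekly usage review picks up the stays that matter, and contacts, events and protocol-required data must be documented. The resulting evaluable set would be sound.

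The figure of 2 to 25 subjects is an upper bound under assumed stay rates and lengths. It requires every site to disregard a written instruction and no subject to use the device in hospital, although the device is intended for hospital use as well. Even then the margin of error goes only to 0.256 h. The conclusion rests on sites doing what sections 11.5, 12 and 14.1 and Appendix I already ask. It would weaken only if the eCRF and site records held no stay dates at all, which the documents do not show.

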11.6. Device and Subject Disposition

When the subject completes their participation in the CAT-PEF Feasibility Study, the AirCurve device must be dispositioned and the subject must be referred for further management.

- If the subject wishes to keep their device and continue ASV therapy, they may do so and should be referred to the appropriate sleep care team for continued management
- If the subject does not wish to continue therapy, they should be referred to the appropriate sleep care team for discussion of options for treating their SDB

Document the device disposition in the eCRF. If the subject does not continue therapy (or has left the study for other reasons, such as death), the device must be returned to the clinical site either at a clinic visit or by mail. Return labels will be provided by the sponsor.

12. SAFETY

The investigator is responsible for monitoring the safety of subjects enrolled into the study at the study site. The investigator or qualified designee will enter the required initial and follow-up information regarding events on the appropriate eCRF within the EDC system. Investigators are responsible for following all serious adverse events (SAEs) until resolution, stabilization, or the event is otherwise explained, and to report serious adverse events as well as serious injury or death that were related to (caused by or contributed to) the AirCurve devices in accordance with their local IRB/EC requirements. Investigators should follow usual clinical practice at their institutions for reporting serious events to the regulatory authorities.

12.1. Hospitalization

For this protocol, the definition of hospitalization is in-patient care of more than one calendar day (overnight admission). The number of hospitalizations the occurred during a subject's participation in the study will be recorded at the final visit.

12.2. Labeled Adverse Device Effects

Expected adverse device events are determined to be mild and are related to the interface (mask) between the device (AirCurve) and the subject. In this study any skin or eye irritation that is transient (ie, resolves within 24 hours following device use and requires no medical intervention), will not be classified as an adverse device effect.

Mask

- Mild skin irritation around the nose and forehead from the mask
- Mild facial abrasions from ill-fitting mask interface
- Eye irritation, caused by leakage of air from the sides of the mask

Flow Generator

- Drying of the nose, mouth, or throat
- Nosebleed
- Bloating
- Ear or sinus discomfort
- Eye irritation
- Skin rashes

13. STATISTICAL ANALYSIS

This study aims to evaluate the adherence to ASV therapy in HFrEF patients with moderate to severe SDB. Descriptive summaries, including means, standard deviations, medians, 25th, and 75th percentiles will be presented for continuous variables; the number and frequency of subjects in each category will be presented for nominal variables. Analyses will be performed using SAS Version 9.3 or later.

13.1. Justification of the Sample Size

The sample size has been determined to estimate the primary objective (the mean usage in hours per night) with sufficient precision. A sample size of 160 evaluable subjects yields a margin of error equal to 0.25 hours per night or less, when the confidence level is 95% and the standard deviation of usage is 1.6 hours per night or less (as observed in a similar study of myAir⁹). Subjects not meeting the evaluability criteria of at least 4hrs ASV usage per day (24hr period) for 70% of the days enrolled (excluding days spent in the hospital) within the first 30 days of therapy initiation, will be discontinued from the study. Assuming that 60% of the study subjects will be evaluable, 266 (which can be rounded up to 300) subjects are expected to be initially enrolled in the study.

13.2. Primary endpoint analysis

The mean usage and its 95% confidence interval will be estimated.

13.3. Secondary endpoint analyses

The mean change in KCCQ-12 scores and its 95% confidence interval will be estimated. The morbidity rate (the average number of hospitalizations per subject) and its 95% confidence interval will be estimated.

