	
 3. Sustained systolic blood pressure <80 mmHg at baseline 4. Complex congenital heart disease 5. Constrictive pericarditis 6. Chronic hypoxemia as evidenced by sustained oxygen saturation ≤ 85% at rest during the day or at start of nocturnal oximetry recording or regular use of oxygen therapy (day or night) 7. Transient ischemic attack (TIA) or Stroke within 3 months prior to study entry 8. Definite clinically evident acute myocardial infarction within 3 months of study entry 9. Known amyloidosis, hypertrophic obstructive cardiomyopathy, or arteriovenous fistulas 10. Moderate or greater valvular heart disease as the primary reason for heart failure 11. Pregnant, or planning to become pregnant during the study period 12. In the opinion of the investigator, the index acute decompensated HF event was due primarily to uncontrolled AFib with fast ventricular response rate 13. Inability to comply with planned study procedures
Primary Endpoints	ASV Adherence rate (average hours used per day) at 3 months
Secondary Endpoints	
 • Feasibility of study conduct as measured by recruitment rate (subjects enrolled per month) by site, reasons for screen failures, and where in the hospital system patients are recruited (eg, HF clinic, general cardiology, etc) • Change in quality of life as measured by the Kansas City Cardiomyopathy Questionnaire (KCCQ-12) • Number of hospitalizations for any reason following study entry • Death for any reason during study participation
Scheduled follow up	
For evaluation of the primary and secondary endpoints, subjects will be followed for a period of 3 months (12 weeks).
 
 • Visit 1 will occur at baseline for device set-up and KCCQ-12 • Visit 2 will occur at 12 weeks for disposition of device, KCCQ-12, and determination of hospitalizations and death

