7.2.2. Number of Subjects

Up to 300 subjects will be initially enrolled in this study. For endpoint evaluation, 160 evaluable subjects are required. For the purposes of this study, an evaluable subject is one with ASV usage of at least 4hrs per night for 70% of the study nights, excluding nights hospitalized after 30 days (1 month) of ASV usage.

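### The hospitalization average in Section 13.3 has no time at risk and no named analysis set, although an assumed 40% of subjects stop at about day 30 of 12 weeks

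*Combined protocol and SAP*

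**What the plan says.** The analysis rule in Section 13.3 is "The morbidity rate (the average number of hospitalizations per subject) and its 95% confidence interval will be estimated". It mentions no person-time, offset or censoring rule and does not say which subjects enter.

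The follow-up in the Protocol Summary (Section 4) is uniform: "For evaluation of the primary and secondary endpoints, subjects will be followed for a period of 3 months (12 weeks". Other sections make it unequal by design:

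- Section 10.5, adherence monitoring at 30 days: "Subjects not meeting adherence criteria will be discontinued from the study".
- Section 11.5, for those subjects: "Record the number of hospitalizations and date of discontinuation on the end of study eCRF". No later contact is described.
- Section 12.1 limits the count to events during a subject's "participation in the study will be recorded at the final visit".
- Section 13.1 sizes the loss: "Assuming that 60% of the study subjects will be evaluable". That leaves 40% who stop at about day 30.

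The nearest statement on an analysis population is in Section 7.2.2: "For endpoint evaluation, 160 evaluable subjects are required". It does not say whether the hospitalization average is confined to those subjects.

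Death, also a secondary endpoint, has no entry in Section 13.3. It falls under the general rule of Section 13, that "the number and frequency of subjects in each category will be presented for nominal variables".

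**The concern.** The plan creates two observation windows, about 30 days for subjects who fail the adherence rule and about 84 days for the rest. It then divides events by subjects as if the windows were equal. Early stopping here is required by the protocol and expected in a large share of subjects, so it is more than incidental dropout.

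If everyone is counted, the result is neither a 30-day nor a 12-week figure, and its size depends on how many subjects fail the rule. Because Section 4 gives 12 weeks of follow-up for the secondary endpoints, a reader would probably take it as a 3-month figure. If only evaluable subjects are counted, the windows are equal but the group has been selected on early adherence. Section 13.3 does not say which applies, so the choice could be made after the data are seen.

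The stake is modest: a correct description of morbidity in this population. Section 5.1 looks ahead to a phase III trial with morbidity and mortality endpoints. Using these rates to plan it is possible, but the documents do not state that use.

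**Working it through.** **The plan's own figures.** Section 13.1: 160/0.60 = 266.7, against the stated 266. Margin of error: 1.96 × 1.6/√160 = 0.248 hours, within the stated 0.25. Both reproduce apart from rounding, so 60% is the working evaluable share.

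**Inputs from the protocol.** Evaluable share p = 0.60 (13.1); stopping at day 30 (11.5); full follow-up of 12 weeks = 84 days (Section 4); visit windows of ±2 days and ±2 weeks (10.6).

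**Base case, all subjects, constant rate equal in both groups.** Expected counts are proportional to days observed.

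- Mean days = 0.6 × 84 + 0.4 × 30 = 62.4.
- Ratio to the 12-week value = 62.4/84 = 0.743, or 26% low.
- 70% evaluable: (58.8 + 9)/84 = 0.807, 19% low.
- 50% evaluable: (42 + 15)/84 = 0.679, 32% low.
- Over the visit windows, measured against the actual length of follow-up: 22% low (day 32, day 70) to 29% low (day 28, day 98).

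**Departures from a constant, equal rate (assumed; the documents give no rates).** Let the rate in the first 30 days be k times the later rate, and let non-adherers have r times the rate of adherers. With p = 0.6:

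- F = 30k + 54 (12-week count per adherer, in units of the later daily rate)
- True all-subject mean T = 0.6F + 0.4rF
- 13.3 average over all subjects A = 0.6F + 0.4r × 30k
- Pooled person-time rate scaled to 84 days P = (A/62.4) × 84
- Evaluable-only average = F

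| Scenario | A/T | P/T | F/T |
|---|---|---|---|
| k = 1, r = 1 | 0.743 | 1.000 | 1.000 |
| k = 2, r = 1 | 0.811 | 1.091 | 1.000 |
| k = 3, r = 1 | 0.850 | 1.144 | 1.000 |
| k = 1, r = 1.5 | 0.679 | 0.913 | 0.833 |
| k = 2, r = 1.5 | 0.763 | 1.027 | 0.833 |
| k = 1, r = 0.75 | 0.786 | 1.058 | 1.111 |

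Example, k = 3: F = 144; A = 86.4 + 36 = 122.4; A/T = 122.4/144 = 0.850; P/T = (122.4/62.4) × 84/144 = 1.144.

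A raised early rate is plausible, because Section 10.4 requires consent within 14 days of the acute encounter.

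**Direction of the dependence on adherence.** A non-adherer contributes 30kr and an adherer F. More non-adherence lowers the all-subject average only while 30kr < F, that is r < 84/30 = 2.8 at k = 1, or r < 114/60 = 1.9 at k = 2.

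**Death.** At an assumed 3% 12-week risk, constant hazard and 300 subjects, about 7 deaths would be observed (6.70/300 = 2.2%). That is too few to justify more than a simple description.

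**The case against.** The strongest reply is that Section 7.2.2 ties endpoint evaluation to the 160 evaluable subjects and Section 4 sizes the study on them. On that reading day-30 stopping causes no shortfall, and the 26% does not arise. This stands as a fair reading. It is not the only one: Section 11.5 has the hospitalization count recorded for discontinued subjects, which would have little purpose if they were never analysed. A reader might infer that the plan will understate morbidity by a quarter. The documents do not support that, because they leave the set open.

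Second, counting over participation matches Section 12.1 and the death endpoint in Section 4, and the plan never names a 12-week rate as its target. That is true, but a per-subject average over windows of such different length has no clear meaning without the follow-up time beside it.

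Third, the replacement is imperfect. If early rates are tripled, the pooled rate is about as far above the truth (14%) as the Section 13.3 average is below it (15%). This stands and must be declared. In the other scenarios tabulated the pooled rate is closer.

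Three further inferences go too far. More non-adherence does not always lower the reported figure (see the 2.8 and 1.9 limits). How often the planned interval would contain the 12-week mean depends mostly on the event rate, which the documents do not give. And no treatment contrast is biased, because the study has a single arm.

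**Conclusion.** The concern holds in a conditional form. Section 13.3 lacks both a time at risk and an analysis set, in a design that builds in unequal follow-up. If all subjects issued a device are counted, the average is about 26% below a 12-week value, given 60% evaluable, stopping at day 30, and a constant rate equal in adherers and non-adherers. It is low in every scenario tabulated, by 15% to 32%. If only evaluable subjects are counted, there is no shortfall from day-30 stopping, but the figure does not describe everyone treated. Against all subjects it would be 17% low if non-adherers have 1.5 times the rate, and 11% high at 0.75 times.

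Severity is low. The endpoint is secondary and descriptive, the primary endpoint is unaffected, and no test or decision depends on it. The event-rate patterns are assumptions; the evaluable share and the follow-up times come from the protocol.

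**What to change.** Amend Section 13.3 as follows.

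1. Name all subjects issued a device as the analysis set for hospitalizations and death.
2. Report hospitalizations per person-time, counted from device issue to death, discontinuation or Visit 2 and scaled to 12 weeks, with a 95% interval from a subject-level robust variance.
3. Beside it, report the 12-week average in evaluable subjects, labelled as such.
4. Report deaths as n/N with total follow-up time. A Kaplan-Meier analysis is not needed for so few events.

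The cost is a few sentences. Section 11.5 already has the count and discontinuation date recorded for discontinued subjects. A date of death is not named as a field, but Section 17.1 requires death notes.

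State the limits with the result. The pooled rate is about 9% high if early rates are doubled and 14% high if tripled. It is about 9% low if non-adherers have 1.5 times the rate. Splitting the rate at day 30 would remove the error from early clustering when the two groups have equal rates. It needs admission dates, and Sections 11.5 and 12.1 ask only for the number of hospitalizations, so this is optional. Extra 12-week calls to discontinued subjects are not required for a descriptive endpoint.
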